Study Title: Load Modification Versus Standard Exercise to Inform Treatment for Individuals With Greater Trochanteric Pain Syndrome.

NCT: NCT03571971

Date: January 31, 2022

Approach:

Overview: This pragmatic, feasibility randomized controlled trial (RCT) will consist of up to 64 adult women and men (ratio of approximately 4:1, respectively) between the ages of 18 and 70 who are diagnosed with unilateral greater trochanteric pain syndrome (GTPS) during their initial physician evaluation within the Jameson Crane Sports Medicine Institute physician clinics at The Ohio State University Wexner Medical Center (OSUWMC). All patients will have their standard clinical evaluation with their physician. The group of patients invited to participate in this study will be individuals who meet our clinical diagnostic criteria for GTPS who do not have systemic health or serious musculoskeletal disorders or recent treatment for their hip pain (Table 1). Members of the study team involved in recruitment and consenting will use a two-part process to ensure eligibility using the "Patient Screen Checklist" and the "Eligibility Criteria Checklist," described in detail in the Standard Operating Procedures document. The baseline study visit will occur immediately following the standard clinical examination with the physician.

Table 1. Eligibility Table

Inclusion Criteria	Exclusion Criteria

Ages 18-70, with a unilateral diagnosis of GTPS with:
 
 • Lateral hip pain, worst over greater trochanter, for ≥ 3 months • Pain with palpation over greater trochanter • Average pain intensity of $\geq 4/10$ most days of the week 	
Any of the following treatments within the last 3 months:
 
 • corticosteroid injection in the affected hip • physical therapy or other skilled exercise intervention by a medical or rehabilitation professional

+ Single leg stance for 30 seconds (lateral hip pain reproduced: +LR of 12.2 for MRI-confirmed GTPS (Grimaldi 2017, BJSM), OR at least one of the following clinical examination criteria:
 
 1). + Hip FADER test ($\geq 2/10$ pain with 90° passive flexion, adduction, external rotation) 2). + Hip FADER-R (lateral hip pain reproduced with resisted internal rotation in FADER position) 3). + Passive hip adduction in sidelying (lateral hip pain reproduced with overpressure into hip adduction) 4). + Adduction with resisted isometric abduction (lateral hip pain reproduced with resistance in adduction position) 5). + FABER (lateral hip pain reproduced with flexion, abduction, external rotation) 	
Any of the following concomitant impairments or conditions:
 
 1). Known or observed advanced spine, hip, knee, or ankle joint pathology, including: 
 • Spinal or lower extremity surgery within the last 6 months • Imaging data showing Kellgren Lawrence grade ≥ 2 in any lower extremity joint with concurrent complaint $\geq 2/10$ most days of the week. • Groin pain as the primary hip pain complaint $\geq 2/10$ most days of the week. • <90 degrees of active hip and knee flexion bilaterally • <0 degrees of active ankle dorsiflexion 2). Systemic inflammatory diseases, or any systemic disease that affects the nervous or musculoskeletal system or uncontrolled diabetes, or active malignancy 3). Individuals who cannot tolerate or should not assume the positions required for the exercises for any reason other than hip discomfort

FADER, flexion adduction external rotation; FABER, flexion abduction external rotation

As part of the clinic-based testing for the study, participants will be asked to (1) complete online surveys with validated patient-reported questionnaires about their pain and function. The single-session of education and instruction (load modification vs standard exercise) will be performed by a licensed physical therapist immediately after the testing procedures are complete. Participants will undergo the same clinic-based testing protocol at the 4-week follow-up prior to their visit with the physician in the Jameson Crane Sports Medicine Institute at OSUWMC. For 4-weeks following the initial evaluation and clinic-based testing, participants will be asked to complete weekly online/telephone surveys to document their hip pain and function as well as their compliance with the prescribed home exercise program. Key variables of interest (Table 2) include the Global Rating of Change scale¹⁸ and the Numeric Pain Rating Scale^{18,33,34}. The other secondary variables of interest will help us more completely assess the effect of the proposed program hip function questionnaires, overall function,³⁵⁻³⁷ activity level,³⁸ and self-efficacy.³⁹

Table 2. Variables of Interest

[figure not shown]
Primary VOIs	Secondary VOIs
Global Rating of Change (GROC) (Mellor 2016)	Frontal plane kinematics of the trunk, pelvis, hip, and knee during a single leg squat
Numeric Pain Rating Scale (NPRS) (Farrar 2010, Fearon 2017, Mellor 2016)	Victorian Institute of Sport Assessment for Greater trochanteric pain syndrome (VISA-G) (Fearon 2014)
	Pain Self-Efficacy Questionnaire (PSEQ) (Nicholas MK 2007)
	Patient Acceptable Symptomatic State question (PASS) (Levy 2016, Chalal 2015)
	Patient Reported Outcomes Measurement Information System (PROMIS) Bank v2.0 Physical Function
	Tegner Activity Level Scale (TALS) (Mohtadi 2012)

A. Sample size estimation:

To inform our sample size estimation for this feasibility randomized controlled trial, we used the available literature which reported a 7% treatment success rate at 4-weeks following a single, standard exercise session (ie. non-load modifying)⁶ and the hypothesized 70% treatment success rate following an 8-week to a supervised load modification program.¹⁸ Conservatively, we estimated that the standard exercise (SE) group and load modification (LM) group would have a 20% and 50% success rate, respectively. **With one-side type I error=0.1, power=80%, and allocation ratio is 1:1, we will need 22 participants in each group (total N=44). We will recruit 64 individuals with GTPS to account for up to 30% attrition over the course of the study due to drop-out.** To fully recruit the study after proper regulatory approval is in place and staff are trained, we anticipate a 15-month recruitment time-frame for the 60 participants. This factors in a recruitment rate of 5 participants per month (see Letters of Support/Collaboration), from an eligible 10 (minimum 50% recruitment rate).

Recruitment and Informed Consent (Figure 1): Prior to enrollment, written informed consent will be obtained from all potential participants after information about the purpose, methods, and demands of the study is provided both verbally and in writing (via the consent documentation) to the participant. The participants for this trial will be recruited from the Jameson Crane Sports Medicine Institute physician clinics at OSUWMC during their on-site medical visit. Once the treating physician confirms GTPS diagnosis through our standardized and validated clinical examination process (Table 1, Inclusion Criteria),^{18,31} the study recruiter will then discuss the study opportunity with the patient and proceed with the consenting process when appropriate.

All participants will be provided verbal and/or written information (depending on preference) detailing the purpose of the study, type of testing and treatment involved, and potential risks and benefits of participation. Participants will be given time to ask questions and determine their interest in participation without coercion. Patients will be informed during the recruiting process, that if they consent to study participation, they cannot receive a corticosteroid injection that day or during the 4 weeks of the trial. A 4-week follow-up visit to the physician is standard of care for patients with GTPS seen in the Jameson Crane Sports Medicine Institute. This allows physicians to evaluate the effects of common treatments like medication, injections, 'wait and see' advice, and/or physical therapy; at that time, they determine next step interventions based on the initial treatment response. Our research will work within this same 4-week 'trial' period during their regularly scheduled doctor's visits to provide one of two different types of exercise education.

Patients who refuse to forgo injections for 4 weeks will be excluded from the study. Individuals who, for medical reasons, cannot tolerate or should not assume the positions required for the exercises for any reason other than hip discomfort will be excluded. Patients must enroll on the same day as the visit with their physician in order to receive the intervention; however, they do not have to complete the REDCap questionnaires during that visit. All participants will have the option to complete their questionnaires via a unique link to their personal survey or verbally by phone; the online link will be sent to them via email to be completed at their earliest convenience. The participants will be required to sign the IRB-approved consent and HIPAA forms prior to participation in the study.

B. Randomization, concealed allocation, and blinding: A randomization list will be generated and secured with the study biostatistician prior to the start of the study. It will contain study-specific unique identifiers (ie. GTPS1, GTPS2, etc) and a binary code for treatment group (ie. 0 or 1). A copy of this list will be provided to the Sports Medicine Clinical Research Manager who provides administrative support to all clinical trials in the Sports Medicine Institute. The Manager will determine the group assignment (e.g. 0 = LM, 1 = SE) independent of the biostatistician and the PI. The PI will put together 30 concealed envelopes for each treatment group that contain the group assignment and the appropriate exercise program instructions (SE vs LM) and provide these to the

Manager. The Manager will then label, seal, and place them in a drawer in the physician. The Manager will not be involved in the recruitment, testing, or analysis involved with this trial. She will be the only person with the UID, randomization order, and treatment allocation data all in one place. These data will be stored under lock and key in the private office of the Manager, and in a password-protected file, accessible only to the Manager.

After consent, participants will proceed with testing by a blinded tester. Randomization and group allocation will occur immediately following testing. After testing, the tester will inform the treating physical therapist of group (e.g. 0 vs 1). The drawer with the concealed/sealed envelopes will be accessible to the treating physical therapist and the physicians. The treating physical therapist will select the next available envelope from the appropriate group (0 vs 1) and proceed with the assigned treatment; only when she or he breaks the envelope seal will she or he know the group assignment (LM vs SE).

C. Blinding: Investigators involved in the participant testing and statistical analysis of the outcome variables of interest will be blinded to group allocation. The treating physicians, physical therapist interventionists and patients cannot feasibly be blinded to treatment arm. Participants will not be informed of the study hypotheses and unblinded investigators will not share group allocation information with the blinded investigators. All references to group assignment in other research documentation (ie. REDCap™, video data collection form) will be coded (ie. '0' and '1') to maintain blinding. One trained tester will consent and perform baseline and 4-week follow-up testing. At the 4-week follow-up, the physician will re-evaluate the participant with the clinical diagnostic criteria and discuss their compliance and response to the home exercise program. As is consistent with standard of care, the physician and patient will determine the next course of treatment. The treatment plan will be entered using custom coding (ie. 'smart phrases') to allow discrete data to be queried. Statistical analysis will be performed by the blinded study biostatistician with input from the PI (see Statistical Analysis Plan). After the physician finishes his/her visit with the participant, the tester will proceed with the 4-week follow-up testing and will remind the participant she or he is blinded to treatment and cannot receive any information about the group to which they have been assigned.

D. Clinic-based testing: Baseline testing and treatment will occur in the clinic, immediately following the physician evaluation and confirmation of GTPS diagnosis, for all patients who consent to participate in the study. The clinic-based testing sessions will occur at baseline (immediately after randomization) and at the 4-week clinical visit by a blinded tester. These testing sessions will take about 10 minutes for the questionnaires. Clinic-based testing will include patient-reported questionnaires using Research Electronic Data Capture (REDCap™) survey. REDCap™ is a secure, web-based application that supports data capture, auditing, and exporting⁴⁰ to gather baseline data with regard to their pain and level of function⁴¹ and is hosted at The Ohio State University. Participants will be given the option to complete the survey on either our research handheld tablet (iPad) or laptop or desktop provided by the researcher.

E. Intervention: The single physical therapy educational and instructional session will occur at baseline, immediately following the clinic-based testing. This session will be administered by the unblinded physical therapist interventionists who is trained to administer these protocols. **Participants will receive either (1) standard exercise education and instruction (SE) or (2) load modification education and instruction (LM), based on their treatment group randomization.** Standard exercise education includes exercises currently prescribed by physical therapists, like stretching and strengthening activities. Participants randomized to the load modification group will undergo approximately 5 additional minutes of education and instruction about their posture and movement modifications and will also be provided an information sheet with text and pictures (see Appendix: Supplements). Both groups will be instructed to perform the home exercise program once per day, performing Level 1 activities for the first two weeks and Level 2 activities for the last two weeks. (see Appendix. Supplements - Home exercise programs for both groups). Both groups will receive handouts with pictures and detailed instructions for each of their exercises.

a. Home exercise program (HEP): Both protocols were modelled after current literature for a standard lower extremity exercise program for GTPS and a load modification program. The load modification program from Mellor and colleagues (2016) was further adapted to include exercise dosage shown to be effective in

patellar tendinopathy trials.^{29,30} The HEP will be instructed and guided by the physical therapist, in combination with practice by the patient, and demonstration by the therapist, if needed. It is expected that program instruction will take about 15-20 minutes in both groups and that the home programs themselves will take between 15-20 minutes. The physical therapist will provide standardized cueing to optimize technique. Participants will be provided opportunities to ask questions during the session and provided a written home program with text and pictures for the patient to follow. These instructions, including the pictures will be made available online through REDCap™, along with instructional videos to provide the participant an additional resource to clarify technique.

b. Activity modifications instructions for the load modification group: This instruction will take approximately 5 additional minutes based on our use of this handout in our physical therapy clinic with patients with GTPS for the past 2 years.

i. **Posture and movement handouts:** The physical therapist will share the handout (Appendix 2. Supplements – Lateral Hip Pain Activity Modifications) with the participant, asking them to identify any of the movements or postures (ie. sitting with legs crossed, iliotibial band stretching) that are common to their daily activities. Patients will be educated as to how each contributes to increased pressure on the lateral structures of hip and can cause pain. The physical therapist will review, demonstrate, and provide feedback on all items relevant to the participants' daily routine.

ii. **Using pain as a load modification guide:** Participants in the load modification group will be instructed not to exceed 5 out of 10 on the NPRS during the exercises, and proceed with training as long as this pain intensity during exercise does not increase their pain in within the next 24 hours.¹³

iii. **Changes to activity level:** participants in the load modification group who report >5/10 pain with exercise that does not change or is worse the next day will be advised to reduce their physical exercise activity (ie. walking, hiking, running).¹³ Participants in the load modification group will also be instructed to modify activity level as needed to avoid increasing pain or stiffness each week. Participants randomized to the standard exercise group will be instructed to avoid the painful physical exercise activity for the duration of the 4-week program (ie. "If it hurts, don't continue to do it. Focus on these few exercises for the 4 weeks). Activity level will be monitored using the Tegner Activity Level Scale on a weekly basis over the 4-week intervention.⁴³

F. Weekly online/telephone surveys: Participants will be asked to complete a REDCap™ survey (Appendix 2. Supplements – Weekly Survey) each week until their follow-up visit to the Jameson Crane Sports Medicine Institute for study testing and their clinical visit. This weekly survey will include the GROC, the NPRS, and home exercise program compliance questions. It will also include questions about any treatment they have received or injuries they have had that may affect the outcomes of interest.

Though not the primary focus of this feasibility trial, we will invite all participants to complete follow-up REDCap™ surveys at 3 and 6 months post initial intervention to gather information about current pain level, function, and activity level. Participants will not be asked to complete any home exercise program compliance data or report changes to their care or any new injuries. With IRB approval, we will obtain information regarding subsequent treatments and procedures from the participants' electronic health record with the goal of providing us relevant preliminary data to inform the variables of interest for the future clinical trial.

Safety stopping rules:

We anticipate a small proportion of the participants in each group (<15%) may experience an increase in symptoms with participation in this trial. Thus, we will employ safety stopping rules as described in detail in the Human Subjects document.

G. Data management

a. **Personal Health Information (PHI):** The participant's medical chart information, REDCap™ data, and 2D videos all contain PHI. All PHI relevant to the patient's hip condition is collected and maintained within the participant's medical chart (IHIS). These PHI data are accessible only by the approved, unblinded researchers who have undergone IHIS training within OSUWMC. REDCap™ data is encrypted and sits behind OSUWMC's firewall. Data will be coded with a unique-identifier (UID) and the file which links the UID to the patient's personal

health information (PHI) will be kept on a secure server behind the OSUWMC firewall and password-protected. Only research team members with user privileges (approved by the PI) have access to this database via username and password. When REDCap™ data are exported to files for analysis, they will be exported without PHI data unless the analysis requires it and the PI approves. These files will be maintained on our secure laboratory server behind OSUWMC firewall; it is accessible only to members of the research team. 2D video will be collected with a GoPro. All videos will be transferred within 24 hours from the GoPro to the (1) laboratory server within a separate, password-protected folder on our server, accessible only to investigators blinded to treatment group, and (2) REDCap. 2D videos will be deleted from the GoPro after successful transfer to the server. As part of the 2D video collection, we will use REDCap to document NPRS scores with the matching video recordings with each task.

Post collection data storage and analysis: A blinded study team member will be responsible for 2D video quality control and creating trial clips for subsequent analysis. Video analysis will begin after the last participant completes their 4-week follow-up. These data will be used to determine measurement variability (intraclass correlation coefficients, standard error of the measurement, and minimal detectable change values) and provide information with regard to changes in movement patterns as a result of program participation. Frontal plane kinematics (peaks and excursions) of the trunk, pelvis, hip, and knee will be calculated (Kinovea version 0.8.15) for each task. Analysis will include the double and single leg static starting postures and peak frontal plane motion (as identified using the joint position tracking function). Lines will be drawn through the long axes of the bones for the shank and thigh, through the ASIS for the pelvis, and from the sternum to the midpoint of the ASIS line (Figure 2). Horizontal and vertical 'lab axes' will be applied to the image to allow calculations relative to pure horizontal (ie. pelvic drop) and pure vertical (ie. trunk lean). Angles will also be calculated with respect to the proximal segment.

Statistical analysis plan:

An intention to treat approach is planned for all analyses, using all participants who were randomized who have available data at 4 week follow-up. Where appropriate, normality will be assessed and non-parametric approaches will be used when assumptions are violated. Demographics and clinical characteristics (ie. age, sex distribution, BMI, baseline pain scores, etc) will be summarized for SE and LM groups, respectively, and compared between the groups using two-sample t-test for continuous outcomes or Fisher's exact test for discrete outcomes.

To evaluate the effect of treatment group allocation on dichotomized treatment success (Aim 1, Hypothesis 1), defined as either: 1) at least 'moderately better' on the Global Rating of Change scale or 2) ≥ 2 point decrease on the Numeric Pain Rating Scale, we will use Fisher's exact test to compare the success rate between SE and LM group. Frontal plane kinematics are a secondary variable of interest (Aim 1, Hypothesis 2). With the available 2D data set, we will compare change scores between groups using independent t-tests and/or effect sizes. These data may serve as preliminary data for future grant applications.

To evaluate study retention rates and treatment adherence (Aim 2) we will use descriptive statistics. We will calculate the number of participants in each treatment group who report completing the home program "most (4+) days of the week" and "mostly as directed" on each of the four (4) follow-up REDCap™ surveys. The retention rate and compliance rate will be calculated with 95% confidence interval using exact binomial for each treatment at each follow-up.

H. Feasibility: We will evaluate the feasibility of a future clinical trial to determine the efficacy of load modification exercises and education in improving post-operative function in patients with GTPS by quantifying:

1. The proportion of recruited participants from the total number (a) screened and (b) eligible
2. Participant adherence as measured by: (1) number of weekly surveys completed (ie. number of surveys completed/total number of surveys, (2) weekly home exercise program compliance (self-reported) over the duration of the study, (3) participation retention/attendance at the 4-week follow-up session, and (5) reasons for drop-out and when it occurred (e.g. participant moved out of the area prior to 4-week follow-up)

I. Potential Problems/Alternative Strategies

1. MRI will not be used to confirm gluteal tendinopathy. Grimaldi and colleagues (2017)³¹ performed a diagnostic utility study of 65 individuals with GTPS that showed pain during a 30 second single limb stance was strongly associated with MRI-confirmed gluteal tendinopathy (+LR = 12.2). Importantly, literature also confirms the high prevalence of MRI-confirmed gluteal tendinopathy in asymptomatic individuals,^{31,44,45} highlighting the absence of a strong association between imaging-identified tissue pathology and the clinical syndrome of GTPS. For the aims of this study, this and other validated clinical tests will be used to identify individuals with GTPS. We accept that a small, but insignificant proportion of enrolled participants with clinical indicators of GTPS may not have radiologically-confirmed gluteal tendinopathy. We do not anticipate this will affect the results of this study.
2. Treatment success is no different between groups (ie. equally effective or ineffective). Compressive forces of the gluteal tendons onto the greater trochanter increase with poor frontal plane control of the hip and pelvis. If is unexpected that modification of these loads through postural and activity modifications and targeted exercises would not be significantly more effective than exercises that disregard this mechanism. However, the lack of effect may indicate the need for more frequent, supervised intervention. If both groups demonstrate equal success, these data would still support our proposed model of a 'physical therapy first' approach.
3. Hip abduction weakness is a clinical feature of GTPS and strength gains may be a critical metric of program success. Hip abduction strength will not be measured, but is associated with poor frontal plane pelvic and hip control during a squatting task. We concede that movement changes may be associated with strength improvements, but contend that improvements in strength do not ubiquitously translate to better movement. Thus, we opted to evaluate movement in this preliminary efficacy and feasibility trial.
4. We may be underpowered to see an effect over the 4 week period. The 4-week follow-up period is consistent with clinical practice and the approach to previous studies^{6,22} evaluating the effect of corticosteroid injections. Further, we modelled our treatment approach on robustly designed RCTs^{14,29,30} in other lower extremity tendinopathy that suggest this 4-week period is enough time to see an effect if one exists.

Benchmarks for success

The first benchmark will be full participant enrollment (N=60) within the first 15 months of the study. The second benchmark will be to maintain 80% 4-week follow-up retention rate; we will assess this at the midpoint of recruitment and testing (N=30) and again at final testing of all participants. Finally, our third benchmark of success will be to have <15% adverse events rates as defined per GROC (see Protection of Human Subjects section)

Citations (in order of appearance)

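### The stated 80% power at 22 per group is not that of the planned Fisher's exact test, which has 69% there and first reaches 80% at 28 per group

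*Combined protocol and SAP*

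**What the plan says.** Section A (Sample size estimation) takes success rates of 20% in the SE group and 50% in the LM group, which it calls conservative, and states: "With one-side type I error=0.1, power=80%, and allocation ratio is 1:1, we will need 22 participants in each group (total N=44". No test is named there. It then inflates the total: "We will recruit 64 individuals with GTPS to account for up to 30% attrition over the course of the study due to drop-out".

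The Statistical analysis plan names the test for treatment success (Aim 1, Hypothesis 1): "we will use Fisher's exact test to compare the success rate between SE and LM group". It does not repeat the sidedness or the significance level. The analysis set is defined as "using all participants who were randomized who have available data at 4 week follow-up", so every loss to follow-up reduces the number analysed.

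Under Benchmarks for success, "The second benchmark will be to maintain 80% 4-week follow-up retention rate".

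The enrolment figure varies. The Overview says the trial "will consist of up to 64 adult women and men", and Section A recruits 64. Section A also says "we anticipate a 15-month recruitment time-frame for the 60 participants", the benchmarks say "The first benchmark will be full participant enrollment (N=60) within the first 15 months of the study", and Section B (Randomization, concealed allocation, and blinding) provides 30 envelopes per group.

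**The concern.** A stated power should be that of the test that will be run. Fisher's exact test is conservative in small samples: its actual one-sided error rate can lie well below the nominal level, and power falls with it. A sample size from a large-sample formula will then be too small for the power quoted. The 22 per group carries weight, because it is the number Section A expects to be enough after drop-out and the plan offers no other justification for its sample size.

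Two related gaps add to this. Because the Statistical analysis plan is silent on sidedness, an analyst could report a two-sided p-value, which would lower power further. And whether 60 or 64 are enrolled changes the number analysed and hence the power.

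**Working it through.** **Inputs.** Section A: p₁ = 0.20 (SE), p₂ = 0.50 (LM), one-sided α = 0.10, power 80%, 1:1 allocation, 64 enrolled, up to 30% attrition. Statistical analysis plan: Fisher's exact test in participants with 4-week data. Benchmarks for success: N = 60, 80% retention.

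**Step 1: reproduce the plan's figure.** Pooled normal approximation without continuity correction, with p̄ = 0.35:

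n = [z₀.₉₀ √(2p̄(1−p̄)) + z₀.₈₀ √(p₁(1−p₁) + p₂(1−p₂))]² / (p₂−p₁)²

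= [1.2816 × √0.455 + 0.8416 × √0.41]² / 0.09 = (0.8645 + 0.5389)² / 0.09 = 21.88, so 22 per group.

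The arcsine formula gives 21.77, also 22. The unpooled formula gives 20.54 and the pooled formula with continuity correction 28.15. Attrition: 22/0.7 = 31.4, so 32 per group and 64 in total. Both stated numbers reproduce. That 22 came from an uncorrected approximation is inferred; the document does not say so.

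**Step 2: exact power of the planned test.** For each pair of success counts (x in SE, y in LM), reject if the one-sided hypergeometric p-value is ≤ 0.10, then sum Bin(x; n₁, 0.20) × Bin(y; n₂, 0.50) over the rejected pairs. Maximum size is the same sum with a common rate, maximised over a grid of that rate.

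| Analysed (SE/LM) | How it arises | Power | Maximum size |
|---|---|---|---|
| 22/22 | Section A | 69.1% | 5.5% |
| 24/24 | 60 × 0.8 = 48 | 73.3% | 5.8% |
| 26/25 or 25/26 | 64 × 0.8 = 51.2 | 77.2% or 78.1% | 6.5% |
| 27/27 | | 78.6% | 6.7% |
| 28/28 | first equal split at 80% | 80.6% | 7.0% |
| 30/30 | 60, no attrition | 84.2% | 7.8% |
| 32/32 | 64, no attrition | 85.9% | 6.7% |

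At 22 per group the test uses at most 5.5% of its 10% allowance, which explains the loss of power.

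**Step 3: random drop-out.** The table fixes the split. If each participant is retained independently, starting from equal arms, average power is 76.8% (64 enrolled) and 74.2% (60 enrolled) at 80% retention. At 70% retention it is 71.1% and 68.3%.

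**Step 4: sidedness.** If the test were run two-sided, power at 22 per group would be 55.0% (α = 0.10) or 43.2% (α = 0.05). At 24 per group it would be 60.9% or 49.3%.

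**Step 5: an exact alternative.** Boschloo's one-sided test at 0.10 has 78.5% power at 22 per group (maximum size 9.7%) and 80.2% at 23 (9.9%).

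**Step 6: sensitivity to the assumed rates** (Fisher, one-sided 0.10, 22 per group):

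| SE vs LM | Power |
|---|---|
| 15% vs 50% | 83.2% |
| 20% vs 55% | 79.5% |
| 20% vs 45% | 57.1% |
| 25% vs 50% | 53.4% |
| 7% vs 50% (Section A's literature rate for SE) | 96.9% |
| 20% vs 70% (Section A's hypothesised rate for LM) | 97.0% |

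**Step 7: enrolment figures.** Envelopes: 2 × 30 = 60, which cannot serve 64 participants. At Section A's 5 participants per month, 60 take 12 months and 64 take 64/5 = 12.8 months, both within 15.

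**The case against.** This is a feasibility trial. Its three benchmarks (enrolment, retention, adverse events) do not use the test, and Fisher's conservatism protects against false positives. Section A names no test and its 22 follows from a standard formula, so this is an approximation mismatch rather than two statements in open conflict. The gap of about 11 points also applies only to exactly 22 per group, a low point of Fisher's saw-toothed power curve (21 per group has 70.0%). Thirty percent attrition from 64 leaves 44.8; at 45 analysed, power is 71.8% (SE 22, LM 23) or 73.8% (SE 23, LM 22). At the 80% benchmark from 64 the shortfall is only 2 to 3 points, and changing one assumed rate by 5 points can matter more than the choice of test. Section A does state one-sided 0.10, and item 4 of Section I already concedes possible low power.

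Much of this stands as a limit on the consequence. The 11 points belong to the literal 22-per-group statement; at 70% retention from 64 the average shortfall is about 9 points (80 − 71.1). The two-sided figures are conditional on a reading the plan leaves open, not on one it adopts. None of it makes the stated power correct for the named test. Item 4 discusses the length of follow-up, not the test, and uncertainty about the rates does not reconcile 80% with the plan's own 20% vs 50%.

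**Conclusion.** The concern holds. At the plan's own rates, and on the reading most favourable to it (one-sided 0.10), the planned test has 69.1% power where Section A states 80%. At 80% retention with near-equal arms, the shortfall is 2 to 3 points if 64 enrol and about 7 points if 60 enrol. With no attrition there is none.

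These figures rest on independent binomial outcomes, the 20% and 50% rates, and an analysis restricted to participants with 4-week data. They do not depend on how 22 was derived.

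This should be fixed, but it does not threaten the validity of the trial. The missing sidedness alone would be an omission of detail. The conflict between 60 and 64 is real but secondary.

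**What to change.** Before unblinding:

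1. In the Statistical analysis plan, state that the treatment-success comparison is one-sided (LM better than SE) at α = 0.10, as in Section A. The restated power figures depend on this.
2. Keep Fisher's exact test and restate Section A's power as 69% at 22 per group, 73% at 48 analysed, 77–78% at 51 analysed and 80.6% at 28 per group. As an option, name Boschloo's exact test instead and state about 79% at 22 per group and 80% at 23, with maximum size below 0.10.
3. Use one enrolment target in the Overview, Section A, Section B and the benchmarks, and match the envelope count to it: at least 32 per group if the target is 64 with equal allocation.

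The cost is protocol and SAP wording, plus at least four more envelopes if the target is 64. No participants are needed beyond the 64 already planned. The downside is a less favourable stated power, or a less familiar test if Boschloo's is chosen. Securing 80% with Fisher's test would instead need 56 analysed, that is 56/0.8 = 70 enrolled at 20% loss or 56/0.7 = 80 at 30% loss; correcting the plan does not require that.
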